7.4.2. Time to CDP event as measured by EDSS or T25FW

Time to CDP as measured by EDSS or T25FW will be defined by reaching at least 1 of the following 2 types of event for each individual:

- An increase from baseline in EDSS score (≥ 1 point from baseline EDSS, if EDSS at entry is ≤ 5.0 or increase of ≥ 0.5 point, if EDSS at entry is ≥ 5.5), confirmed after at least 12 weeks, **or**
- An increase of at least 20% from baseline in the T25FW test, confirmed after at least 12 weeks

Progression cannot be confirmed during a protocol defined relapse. A similar algorithm to that described for CDP as measured by EDSS will be used for definition and censoring rules of this variable (see Section 7.4.1).

T25FW will be calculated as a mean time of two T25FW trials at each visit. In cases when a patient could not complete a T25FW trial due to the physical limitations a value of 180 seconds will be assigned for that trial (this is the maximal possible value for the T25FW test).

Time to CDP as measured by EDSS or T25FW, confirmed after at least 12 weeks will be analyzed using the ITT population and will include data from all the study assessments done up to seven days after the date of last dose of the study drug (all the following assessments will be excluded from this analysis). This analysis will be performed using baseline adjusted Cox's proportional hazards regression model (SAS® PROC PHREG) in which 1 contrast for comparing laquinimod 0.6 mg to placebo will be constructed. In addition to treatment group, categorical EDSS at baseline (≤ 4.5 or > 4.5), age at baseline, T25FW at baseline, natural logarithm of T2 lesion volume at baseline, and CGR will be used as covariates. The SAS code for this analysis is as follows:

```

PROC PHREG;
  CLASS ARM EDSSBASE CGR;
  MODEL TIME_TO_PROGRESSION*CENSOR(1,2,3)=ARM EDSSBASE T25BASE AGE LT2BASE CGR /
COVB RL;
  CONTRAST 'Laq 0.6 to Plb' ARM 1 / ESTIMATE=EXP;
  WHERE ARM in ('Laquinimod 0.6 mg', 'Placebo'); RUN;

```

In case the above model will not converge due to CGR variable, then CGR will be removed from the model.

The adequacy of the proportional hazards assumption will be confirmed by including a time-dependent covariate of laquinimod 0.6 mg (as dummy variables) by log (time) interaction in the analysis model and testing it at the 5% level. If the proportional hazards assumption will be rejected, the log rank test (SAS® PROC LIFTEST) will be used for statistical inference. The SAS code for checking the proportional hazards assumption is as follows:

```

PROC PHREG;
  CLASS ARM EDSSBASE CGR;
  MODEL TIME_TO_PROGRESSION*CENSOR(1,2,3)=ARM ARMT EDSSBASE T25BASE AGE LT2BASE
CGR ;
  ARMT = ARM*log(TIME_TO_PROGRESSION);
  PROP_HAZARDS_TEST_LAQ_0_6: test ARMT;
  WHERE ARM in ('Laquinimod 0.6 mg', 'Placebo');
RUN;

```

In case the above model will not converge due to CGR variable, then CGR will be removed from the model.

In addition, patients with CDP as measured by EDSS or T25FW will be summarized using descriptive statistics. The time to CDP as measured by EDSS or T25FW will be presented by Kaplan-Meier curves stratified by treatment group.

All analyses presented in the section will be repeated to include both part A and part B when the study is completed.

7.4.3. Change from baseline to week 48 in the T25FW test

Change from baseline in the T25FW test at week 48 will be analyzed using the mITT2 population and will include all the assessments done up to seven days after the last dose of the study drug (all the following assessments will be excluded from this analysis). Since this variable might not follow normal distribution, the ranked values of this measurement will be defined and analyzed using baseline adjusted repeated measures ANCOVA (SAS® PROC MIXED) in which 1 contrast will be constructed in order to compare between laquinimod 0.6 mg and placebo. In addition to treatment group, T25FW test at baseline, week (categorical, 4 levels), treatment by week interaction and CGR will be used as covariates. Additionally, week (categorical) will be specified as a repeated effect and unstructured (UN) correlation matrix will be used to model intra-subject correlation. In case a convergence issue will arise using the UN correlation matrix, (1) AR1 or (2) Compound Symmetry (CS) will be used to enable model convergence (in this order). Due to the fact that the ANCOVA model will use ranked values and not the actual

changes in the T25FW, Hodges-Lehmann estimates will be used in order to present the magnitude of the treatment effect and the corresponding two sided 95% confidence limit.

The SAS code for defining ranked values and performing this analysis is as follows:

1. Ranked values assignment:

```
PROC RANK OUT=RANKED;
  VAR CHANGE T25BASE;
  RANKS CHANGERANK T25BASERANK;
  WHERE ARM in ('Laquinimod 0.6 mg', 'Placebo');
  RUN;
```

2. Repeated measures ANCOVA model:

```
PROC MIXED DATA=RANKED;
  CLASS SUBJID ARM WEEK CGR;
  MODEL CHANGERANK=ARM WEEK ARM*WEEK T25BASERANK CGR;
  REPEATED WEEK / TYPE=UN SUBJECT=SUBJID R RCORR;
  ESTIMATE 'Laq 0.6 to Plb' ARM 1 0 -1 ARM*WEEK 0 0 0 1 0 0 0 -1 / CL;
  LSMEANS ARM*WEEK / PDIFF CL;
  RUN;
```

3. HL estimates:

```
PROC NPAR1WAY HL;
  CLASS ARM;
  VAR CHANGE;
  WHERE WEEK=48 and ARM in ('Laquinimod 0.6 mg', 'Placebo');
  RUN;
```

In addition, actual values of T25FW and changes from baseline to each visit will be summarized using descriptive statistics.

When the study is completed, actual values of T25FW and changes from baseline to each visit will be summarized using descriptive statistics to include both part A and part B. Also, the changes from baseline to each visit will be analyzed using similar statistical methodology as presented in this section for changes from baseline to week 48 in T25FW test.

7.4.4. The number of new T2 lesions at week 48

The number of new T2 lesions at week 48 compared to baseline will be analyzed using the mITT1 population and will include all the assessments done up to one month after the last dose of the study drug (all the following assessments will be excluded from this analysis). This analysis will be performed using baseline adjusted negative binomial regression model (SAS® PROC GENMOD) in which 1 contrast for comparing laquinimod 0.6 mg to placebo will be constructed. In addition to the treatment group, the natural logarithm of T2 lesion volume at baseline, age at baseline and CGR will be used as covariates. The SAS code for this analysis is as follows:

```
PROC GENMOD;
  CLASS ARM CGR;
  MODEL T2LES=ARM LT2BASE AGE CGR/ DIST=NB LINK=LOG TYPE3;
```

```
LSMEANS ARM/ CL;  
ESTIMATE 'Laq 0.6 to Plb' ARM 1 -1 / ESTIMATE=EXP;  
WHERE ARM in ('Laquinimod 0.6 mg', 'Placebo');  
RUN;
```

In addition, the number of new T2 lesions at week 48 will be summarized using descriptive statistics.

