4.2. Modified ITT1 (mITT1) Population

The modified ITT1 (mITT1) is a subset of the ITT population. It will include all patients in the ITT population with at least 1 post baseline PBVC assessment.

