7.5.15. Change from baseline to week 48 in Symbol Digit Modalities Test (SDMT)

Change from baseline to week 48 in SDMT score will be analyzed for mITT2 population using baseline adjusted repeated measures analysis of covariance (ANCOVA SAS® PROC MIXED) in which 1 contrast will be constructed in order to compare between laquinimod 0.6 mg and placebo. The model will be comprised from the treatment group as a class variable (2 levels). In addition to the treatment group, week (categorical, 4 levels), treatment by week interaction, SDMT at baseline, and CGR will be used as covariates. Additionally, week (categorical) will be specified as a repeated effect and unstructured (UN) correlation matrix will be used to model intra-subject correlation. In case a convergence issue will arise using the UN correlation matrix, (1) AR1 or (2) Compound Symmetry (CS) will be used to enable model convergence (in this order). The SAS code for this analysis is as follows:

```
PROC MIXED;
  CLASS SUBJID ARM WEEK CGR;
  MODEL CSDMT=ARM WEEK ARM*WEEK SDMTBASE CGR / SOLUTION CL;
  REPEATED WEEK / TYPE=UN SUBJECT=SUBJID R RCORR;
  ESTIMATE 'Laq 0.6 to Plb' ARM 1 -1 ARM*WEEK 0 0 0 1 0 0 0 -1 / CL;
  LSMEANS ARM*WEEK / PDIFF CL;
  WHERE ARM in ('Laquinimod 0.6 mg', 'Placebo');
RUN;
```

In addition, actual values of the SDMT score and changes from baseline to each visit will be summarized using descriptive statistics.

When the study is completed, actual values of SDMT and changes from baseline to each visit will be summarized using descriptive statistics to include both part A and part B. Also, the changes from baseline to each visit will be analyzed using similar statistical methodology as presented in this section for changes from baseline to week 48 in SDMT test.

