MODEL CHANGERANK= T25BASERANK CGR ARM|WEEK|GENDER;
REPEATED WEEK / TYPE=UN SUBJECT=SUBJID R RCORR;
LSMEANS ARM*WEEK*GENDER / PDIFF CL;
LSMESTIMATE arm*WEEK*GENDER "MALES, WEEK 48, 0.6 MG VS PLACEBO" [-1, 1 2 1] [1, 2 2 1]/CL;
LSMESTIMATE arm*WEEK* GENDER "FEMALES, WEEK 48, 0.6 MG VS PLACEBO" [-1, 1 2 2] [1, 2 2 2]/CL;
RUN;

```

- Repeat the for the secondary endpoint of number of new T2 lesions at week 48 by gender. This analysis will be performed on the mITT2 analysis set and will use the original GENMOD model while adding gender and treatment by gender interaction terms.

```

PROC GENMOD;
CLASS ARM CGR GENDER;
MODEL T2LES=ARM GENDER ARM * GENDER LT2BASE AGE CGR/ DIST=NB LINK=LOG TYPE3;
LSMEANS ARM*GENDER/ CL;
lsmESTIMATE arm*gender "MALE 0.6 MG VS PLACEBO "  [-1, 1 1] [1, 2 1]/exp;
lsmESTIMATE arm*gender "FEMALE 0.6 MG VS PLACEBO "  [-1, 1 2] [1,2 2]/exp;
WHERE ARM in ('Laquinimod 0.6 mg', 'Placebo');
RUN;

```

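### The coded week-48 contrast for the timed walk cannot be estimated, and the by-gender T2-lesion contrast runs opposite to the main one and names another population

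*SAP*

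**What the plan says.** **T25FW, SAP 7.4.3.** The ranking step keeps laquinimod 0.6 mg and placebo only, and week has four levels (12, 24, 36, 48). The week-48 contrast is "ESTIMATE 'Laq 0.6 to Plb' ARM 1 0 -1 ARM*WEEK 0 0 0 1 0 0 0 -1 / CL". The same step also requests "LSMEANS ARM*WEEK / PDIFF CL", and the text says that "Hodges-Lehmann estimates will be used in order to present the magnitude of the treatment effect". The SDMT analysis in 7.5.15 has the same two-arm, four-week layout and codes "ESTIMATE 'Laq 0.6 to Plb' ARM 1 -1 ARM*WEEK 0 0 0 1 0 0 0 -1 / CL".

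**New T2 lesions, SAP 7.4.4.** The count "compared to baseline will be analyzed using the mITT1 population", and the contrast is "ESTIMATE 'Laq 0.6 to Plb' ARM 1 -1 / ESTIMATE=EXP".

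**New T2 lesions by gender, SAP 7.5.21.** "This analysis will be performed on the mITT2 analysis set and will use the original GENMOD model", with gender and its interaction with treatment added. For each sex the contrast puts -1 on ARM level 1 and +1 on ARM level 2, under a label that reads as 0.6 mg against placebo.

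**T25FW by gender, SAP 7.5.21.** GENDER is in the model but not in the CLASS statement. The contrast labelled week 48 uses week index 2, again with -1 on ARM level 1 and +1 on ARM level 2.

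**Percent brain volume change (PBVC) by gender, SAP 7.5.21.** This is offered as example code. Its contrasts refer to TRTPN and SUBVAR, which are not in its model.

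SAP 3.2.3 lists the by-gender analyses as exploratory. They are the stated reason for SAP version 2.0.

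**The concern.** A contrast in a SAP is there to fix the comparison before the code is broken. The one coded for T25FW, third in the hierarchy of SAP 5.3, returns nothing. The SAP gives 9HPT the same method (7.5.14) and the Part B T25FW analyses a similar one, so the error can spread.

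The T2 problem is of another kind, because it returns a number that looks valid. If the exponentiated result is the reciprocal of what its label says, a benefit in one sex reads as harm, or the reverse. Reversing the sign leaves the p-value unchanged, so nothing in the test would give a warning. The population conflict adds a second way in which the by-gender result may not match the analysis it is meant to repeat.

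**Working it through.** The plan gives no figure on this point to reproduce. The check is of the code itself.

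**1. Is the T25FW contrast estimable?** The model has an intercept, ARM, WEEK and ARM*WEEK, plus ranked baseline and region. Let c(i,j) be the coefficient on the cell for arm i and week j. Any estimable function must then have

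- ARM*WEEK coefficient (i,j) = c(i,j)
- ARM coefficient i = sum over weeks of c(i,j)

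The coded interaction terms set c(1,4) = +1 and c(2,4) = -1. The ARM coefficients must therefore be +1 for arm 1 and -1 for arm 2.

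- Two arms, surplus coefficient ignored: ARM is coded (1, 0). Arm 2 has 0 where -1 is needed, so the function is not estimable.
- Three arms: ARM is coded (1, 0, -1). Arm 2 has 0 where -1 is needed, and arm 3 has -1 where 0 is needed, so it is again not estimable.

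Comparing the rank of the design with its rank after the contrast row is added gives the same answer:

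| Contrast | Layout | Rank before | Rank after | Estimable |
|---|---|---|---|---|
| T25FW as coded (7.4.3) | 2 arms x 4 weeks | 8 | 9 | no |
| T25FW as coded, if three arms | 3 x 4 | 12 | 13 | no |
| SDMT (7.5.15) | 2 x 4 | 8 | 8 | yes |
| PBVC (7.2) | 2 x 2 | 4 | 4 | yes |

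**2. What survives for T25FW?** Subtract the week-48 least-squares mean of arm 2 from that of arm 1. The intercept and WEEK terms cancel, leaving ARM (1, -1) and ARM*WEEK (0 0 0 1 0 0 0 -1). That is the SDMT form, element by element, so LSMEANS with PDIFF gives the intended estimate and p-value. In one simulated data set (140 per arm, four visits) both routes gave -0.0282, SE 0.1195, p = 0.8134. The result is one of 8 x 7 / 2 = 28 pairwise differences printed.

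**3. Signs of the arm contrasts.**

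| Contrast | ARM level 1 | ARM level 2 | If laquinimod is level 1 | If placebo is level 1 |
|---|---|---|---|---|
| PBVC (7.2) | +1 | -1 | drug - placebo | placebo - drug |
| T2 main (7.4.4) | +1 | -1 | drug - placebo | placebo - drug |
| SDMT (7.5.15) | +1 | -1 | drug - placebo | placebo - drug |
| T2 by gender (7.5.21), each sex | -1 | +1 | placebo - drug | drug - placebo |

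All four labels mean drug against placebo. No single level order makes both T2 rows right. ARM appears as text in the WHERE clauses, and alphabetical order puts laquinimod first. The first three rows need that order, so under it the by-gender row is the reversed one.

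**4. Size of the reversal.** The printed value is 1 divided by the true ratio. For assumed true laquinimod/placebo ratios (the documents give none):

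- 1/0.60 = 1.67
- 1/0.70 = 1.43
- 1/0.80 = 1.25
- 1/0.90 = 1.11

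**5. Week index for T25FW by gender.** The week-48 bracket is identical to the PBVC one. In PBVC, week has two levels (24, 48), so index 2 is week 48. In T25FW it has four (12, 24, 36, 48), so index 2 is week 24.

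**6. Populations.** mITT1 requires patients "with at least 1 post baseline PBVC assessment". mITT2 (SAP 4.3) requires at least one of a list of clinical assessments, none of them MRI. The two can differ only for patients who have a T2 count but lack either a PBVC value or every listed clinical assessment. The documents do not give their number.

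**The case against.** The case for treating these as minor slips has real support. The T25FW text fixes the comparison, the p-value is available elsewhere in the same step, and a contrast that prints nothing cannot mislead anyone. The SAP never states the ARM order, and all the by-gender least-squares contrasts share one sign pattern, which suggests code taken from a template with another order. The by-gender T2 step also prints arm-by-sex means, from which a careful reader could see the direction. The T25FW by-gender step needs GENDER in CLASS before it can run, so as written no week-24 value can appear under a week-48 label. The PBVC code is only an example. A T2 count and a PBVC come from the same scheduled scan, so the two populations should nearly coincide.

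Most of this stands, and it limits the harm. It does not remove the fault. Whichever order was intended, one of the two T2 contrasts contradicts its label, so naming the order is not enough. Adding GENDER to CLASS alone would make the T25FW step report week 24, with reversed sign in alphabetical arm order, under a week-48 label. The text names two populations for what it calls the same model, and SAP 12 does not list the change.

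**Conclusion.** The point holds and should be corrected, but its reach is limited. The T25FW contrast is not estimable as coded. This assumes that the software ignores surplus coefficients; if it rejects the line instead, there is still no estimate. Neither the p-value nor the effect size for that endpoint is lost.

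The two T2 contrasts conflict under any arm order. That the by-gender one is the reversed one rests on default alphabetical ordering, and the size of the reversal rests on assumed ratios. The mITT1/mITT2 conflict is certain in the text, and its effect on patient numbers is unknown and may be small. The primary analysis is unaffected, and the by-gender analyses are exploratory and outside the hierarchy.

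**What to change.** - **T25FW, 7.4.3:** use `ARM 1 -1` with the same ARM*WEEK coefficients, as for SDMT. Carry this to 9HPT and to the Part B analyses that borrow the method.
- **T2 lesions by gender:** use `[1, 1 g] [-1, 2 g]` for each gender level g, and name mITT1.
- **T25FW by gender:** add GENDER to CLASS and use `[1, 1 4 g] [-1, 2 4 g]`.
- **PBVC by gender:** write the contrast on ARM*WEEK*GENDER with `[1, 1 2 g] [-1, 2 2 g]`.
- **Time to progression by gender:** correct the misspelt GEMDER.
- **All blocks:** state the ARM and GENDER level order once. The bracket forms above take laquinimod as ARM level 1. The gender coding is not given, and if it sorts with females first, the male and female labels are swapped too.

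The cost is a few lines of code and one population name, changed before the treatment code is broken. No new data are needed.

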7.5. Exploratory/Other Efficacy Variables and Analysis

7.5.1. Change from baseline to week 48 in the CVLT-II score

CVLT-II scores will be calculated as a sum of total correct responses from five CVLT-II trials for each patient. If one of the five CVLT-II trials is missing, then the CVLT-II score will be considered missing as well.

Change from baseline in the CVLT-II score at week 48 will be analyzed using the mITT2 population. This analysis will be performed using baseline-adjusted Analysis of Covariance (ANCOVA, SAS® PROC GLM) in which a contrast for comparing laquinimod 0.6 mg to placebo will be constructed. In addition to treatment group, baseline CVLT-II score and CGR will be used as covariates. The SAS code for this analysis is as follows:

```
PROC GLM;  
CLASS ARM CGR ;  
MODEL CCVLT = ARM CVLTBASE CGR /CLPARM SOLUTION;  
LSMEANS ARM /STDERR CL;  
ESTIMATE 'Laq 0.6 to Plb' ARM 1 -1;  
WHERE ARM in ('Laquinimod 0.6 mg', 'Placebo');  
RUN;
```

In addition, the CVLT-II scores and changes from baseline to each visit will be summarized using descriptive statistics.

When the study is completed, actual values of CVLT-II and changes from baseline to each visit will be summarized using descriptive statistics to include both part A and part B. Also, the changes from baseline to each visit will be analyzed using similar statistical methodology as presented in this section for changes from baseline to week 48 in CVLT-II test.

7.5.2. Change from baseline to week 48 in the BVMT-R score

BVMT-R scores will be calculated as a sum of total correct responses from three BVMT-R trials for each patient. If one of the three BVMT-R trials is missing, then the BVMT-R score will be considered missing as well.

Change from baseline in the BVMT-R score at week 48 will be analyzed by applying the same methodology used to analyze the change from baseline to week 48 in the CVLT-II score (see Section 7.5.1). Baseline CVLT-II score covariate will be replaced by BVMT-R at baseline. In addition, the BVMT-R scores and changes from baseline to each visit will be summarized using descriptive statistics.

When the study is completed, actual values of BVMT-R and changes from baseline to each visit will be summarized using descriptive statistics to include both part A and part B. Also, the changes from baseline to each visit will be analyzed using similar statistical methodology as presented in this section for changes from baseline to week 48 in BVMT-R test.

7.5.3. Time to CDP as measured by at least 1 of 4 types of events

Time to CDP as measured by at least 1 of 4 types of events for each individual will be defined if one of the below conditions holds (progression cannot be confirmed during a protocol defined relapse):

- An increase from baseline in EDSS score (≥ 1 point from baseline EDSS if EDSS at entry is ≤ 5.0 , or increase of ≥ 0.5 point if EDSS at entry is ≥ 5.5), confirmed after at least 12 weeks **or**
- An increase of at least 20% from baseline in T25FW test (see Section 7.4.3 for definition), confirmed after at least 12 weeks **or**
- An increase of at least 30% from baseline in the 9HPT test, confirmed after at least 12 weeks **or**
- A decrease of at least 20% from baseline in the SDMT score, confirmed after at least 12 weeks

9HPT will be calculated as a mean time of two 9HPT trials for both dominant and non-dominant hands (4 trials overall) at each visit. In cases when a patient could not complete a 9HPT trial due to the physical limitations a value of 300 seconds will be assigned for that trial (this is the maximal possible value for the 9HPT).

Similar algorithm to that described for CDP as measured by EDSS confirmed after at least 12 weeks will be used for definition and censoring rules of this variable (see Section 7.4.1).

Time to CDP as measured by at least 1 of 4 types of events for each individual will be analyzed using the same methods as described for time to CDP as measured by EDSS in Section 7.4.1. In addition to treatment group, categorical EDSS at baseline (≤ 4.5 or > 4.5), age at baseline, natural logarithm of T2 lesion volume at baseline, T25FW at baseline, 9HPT at baseline, SDMT score at baseline and CGR will be used as covariates.

In case the above model will not converge due to CGR variable, then CGR will be removed from the model.

The adequacy of the proportional hazards assumption will be checked using the same methodology as described for time to CDP as measured by EDSS in Section 7.4.1.

In addition, patients with CDP as measured by at least 1 of 4 types of events will be summarized using descriptive statistics. The time to CDP as measured by at least 1 of 4 types of events will be presented by Kaplan-Meier curves stratified by treatment group.

All analyses presented in the section will be repeated to include both part A and part B when the study is completed.

7.5.4. Time to CDP as measured by EDSS confirmed after at least 24 weeks.

Similar algorithm to that described for CDP as measured by EDSS confirmed after at least 12 weeks will be used for definition and censoring rules of this variable (see Section 7.4.1) with the distinction that the increase in EDSS should be sustained for at least 24 weeks instead of 12 weeks. The methodology and covariates for this analysis will be the same as for the primary analysis, including check of the proportional hazards assumption.

In addition, patients with CDP as measured by EDSS confirmed after at least 24 weeks will be summarized using descriptive statistics. The time to CDP as measured by EDSS confirmed after at least 24 weeks will be presented by Kaplan-Meier curves stratified by treatment group.

All analyses presented in the section will be repeated to include both part A and part B when the study is completed.

7.5.5. The number of new T1-hypointense lesions at week 48

The number of new T1-hypointense lesions at week 48 will be analyzed by applying the same methodology used to analyze the number of new T2 lesions at week 48 (see Section 7.4.4). Natural logarithm of baseline T2 lesion volume covariate will be replaced by natural logarithm of T1-hypointense lesion volume at baseline. In addition, the number of new T1-hypointense lesions at week 48 will be summarized using descriptive statistics.

